**Table 1 Overview of Ocrelizumab Dosing**

Group	1 st Dose a,c		2 nd Dose b,c	3 rd Dose b,c	4 th Dose b,c
	(Weeks 1 – 24)		(Weeks 24 – 48)	(Weeks 48 – 72)	(Weeks 72 – 96)
	Day 1 Infusion	Day 15 Infusion	Week 24 Infusion	Week 48 Infusion	Week 72 Infusion
Ocrelizumab	300 mg IV in 250 mL 0.9% sodium chloride	300 mg IV in 250 mL 0.9% sodium chloride	600 mg IV in 500 mL 0.9% sodium chloride	600 mg IV in 500 mL 0.9% sodium chloride	600 mg IV in 500 mL 0.9% sodium chloride

IV= intravenous.

Note: Before each infusion of ocrelizumab, 100 mg of methylprednisolone IV and an antihistaminic drug will be administered to reduce the potential for infusion-related reactions. Each dose has a duration of 24 weeks. The open-label treatment period consists of 96 weeks of treatment; patients will receive a maximum of 4 doses.

- a The first dosing will consist of two IV infusions separated by 14 days (i.e., Days 1 and 15).
- b Beginning with the second dose, a single infusion of ocrelizumab will be administered.
- c Prior to the next infusion, a clinical evaluation will be performed to ensure that the patient remains eligible for retreatment.

Guidelines for dosage modification and treatment interruption or discontinuation are provided in Section [5.1.4](#).

Any overdose or incorrect administration of study drug should be noted on the Study Drug Administration electronic Case Report Form (eCRF). AEs associated with an overdose or incorrect administration of study drug should be recorded on the AE eCRF.

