This study is a prospective, multicenter, open-label, efficacy and safety study in patients with RRMS who have had a suboptimal response to an adequate course of a DMT. An adequate course of prior DMT is defined as a stable dose of the same DMT administered for at least 6 months. The first dose of ocrelizumab will be administered as an initial dose of two 300-mg infusions (600 mg total) in 250 mL 0.9% sodium chloride each separated by 14 days (i.e., Days 1 and 15) followed by one 600-mg infusion in 500 mL 0.9% sodium chloride every 24 weeks for the remainder of the study duration.

This study will enroll approximately 750 patients. Patients will be assessed for efficacy and safety every 24 weeks as described in the Schedule of Assessments in [Appendix 2](#).

The study will consist of the following periods:

- Screening period: Up to 4 weeks
- Treatment period: Open-label treatment period of 96 weeks (last dose administered at Week 72)
- A follow-up period of at least 2 years, which is independent of the DMT administered

Follow-up Period: Patients who discontinue treatment early will be followed up for at least 96 weeks after the Early Treatment Discontinuation Visit. Patients who complete the 96 weeks Treatment Period and, in agreement with their treating neurologist, decide not to continue in a separate long term extension (LTE) study, will be followed up for at least 96 weeks after the end of the Treatment Period. Patients who decide to leave the study and switch to commercially marketed ocrelizumab, either after completion of the 96 weeks Treatment Period or after early discontinuation of the 96 weeks Treatment Period, will not enter the safety Follow-up Period.

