4.6.2 Adverse Events

For each recorded adverse event (AE), the term entered by the investigator describing the event (the “reported term”) will be assigned a standardized term (the “Preferred Term” [PT]) and assigned to a superclass term (the “System Organ Class” [SOC]) on the basis of the MedDRA World Health Organization (WHO) dictionary of terms.

Treatment emergent adverse events (TEAEs) will be summarized by SOC and PT. At each level of summarization (at least one event, SOC and PT), patients reporting more than one AE will be counted only once. For TEAEs by grade (intensity), the highest grade

will be reported. The table results will be sorted by descending frequency of SOC and PT within each SOC.

Summary of TEAEs will be repeated for the following subgroups, provided that they include at least 50 patients:

- Last DMT prior to study enrolment
 - Interferons (Interferon β 1a, Interferon β 1b, Peg Interferon β 1a)
 - Glatiramer acetate
 - Teriflunomide
 - Fingolimod
 - Dimethyl fumarate
 - Natalizumab

Definitions

Treatment-emergent adverse events (TEAE): AEs with an observed or imputed date of onset on or after the start date of trial treatment. If the onset date of the AE is prior to the day of first dose, the AE will be considered treatment-emergent only if the most extreme intensity is greater than the initial intensity (i.e., the intensity for a given AE increases and its end date is on or after the date of the first dose). An AE with a completely missing, non-imputed start date will be assumed to be treatment emergent unless the AE has a complete, non-imputed end date that is prior to the date of the first dose.

An adverse event will be considered as treatment-emergent in the period “baseline to week 24”, if the AE onset date occurred on or after the start date of trial treatment and before start date of trial treatment + 24 weeks. An adverse event will be considered as treatment-emergent in period “>= week X – week Y”, if the AE onset date occurred on or after the start date of trial treatment + week X and before start date of trial treatment + Y weeks. If the emergence of an AE cannot be clearly assigned to a period, the AE will be considered emergent across all appropriate periods.

Imputation of incomplete date: in order to evaluate if an AE is treatment-emergent, incomplete dates will be imputed as follows:

- If the start date is incomplete:
 - If the day is missing, impute to 01
 - If the day and months are missing, impute to 01JAN

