 - If the date is completely missing, it is considered treatment-emergent
- If the end date is incomplete:
 - If the day is missing, impute to the last day of the month
 - If the day and month are missing, impute to 31DEC
 - If the date is completely missing, it is considered treatment emergent

Serious Adverse events (SAEs): all SAEs including serious MS relapses and serious Infusion Related Reactions (IRRs).

Dose assigned to an AE: only applicable if the AE onset date is on or after the date of the first infusion of that dose but before the first infusion of the next treatment dose. AEs that are reported during the safety follow-up period will be assigned to the last dose received. AEs that start prior to the first dose and worsen during treatment (i.e., treatment-emergent) will be assigned to the first treatment dose.

Output Conventions

All analyses of AE data will be performed using the PTs unless otherwise specified.

For all summary tables, the AEs will be sorted by SOC (in decreasing order of overall incidence) and then by PT (in decreasing order of overall incidence). All summaries and listings of AEs will be based on the ITT population. Summaries of AEs will be generated to summarize the incidence of treatment-emergent AEs only (TEAE and AE are used exchangeable).

A listing of all AEs will be provided, including all relevant information (including -but not limited to- start date, end date and the corresponding study days, related to treatment, seriousness, Grade, treatment-emergence).

Incidence Analysis on number of the events and number of patients with at least one event:

Overview of TEAE, including

- AE
- Serious AE
- Death
- AE with fatal outcome
- Infusion related reaction (IRR)
- Serious infusion related reaction (IRR)
- Infections (using the MedDRA SOC of “Infections and Infestations.”)
- Serious infection (using the MedDRA SOC of “Infections and Infestations.”)
- AE leading to study drug discontinuation (“Drug Withdrawn” for the “Action taken with ocrelizumab due to SAE/AE” field in the “Adverse Event/IRR/MS Relapse” eCRF form)
- Serious AE leading to study drug discontinuation (“Drug Withdrawn” for the “Action taken with ocrelizumab due to SAE/AE” field in the “Adverse Event/IRR/MS Relapse” eCRF form)
- AE leading to dose modification/interruption
- Serious AE leading to dose modification/interruption

- AE related to study medication,
- AE of Grade ≥ 3

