An epoch summary (baseline to week 24, week 24 to week 48, and week 48 to week 96) of TEAEs will be repeated including the number of events and number and proportion of patients with adverse events emerging and serious AE in each of the period (baseline to week 24, \geq week 24 – week 48, \geq week 48 – week 96) will be provided.

Summary tables presenting the number of patients who experienced a TEAE will be summarized by SOC and PT for the following:

- **All TEAEs**
An epoch summary (baseline to week 24, week 24 to week 48, and week 48 to week 96) of TEAEs. The number and proportion of patients with adverse events emerging in each of the period (baseline to week 24, \geq week 24 – week 48, \geq week 48 – week 96) will be provided.
- If an AE cannot be allocated to
- **Most Common TEAEs** reported by 5% or more of patients
- **TEAEs related to study drug** (“Yes” for the “Even suspected to be caused by ocrelizumab?” field on the “Adverse Event/IRR/MS Relapse” eCRF form)
- **TEAEs by Intensity Grade** (“1”, “2”, “3”, “4”, “5” for the “AE most extreme NCI CTCAE grade” field in the “Adverse Event/IRR/MS Relapse” eCRF form). Multiple occurrences of the same event within a patient will be counted once at the greatest intensity/highest grade for this PT. For AEs leading to death, the most extreme intensity will be overwritten by Grade 5 (death). Any AEs and the SOC overall rows of the summary table will count patients according to AEs by intensity (grade).
- **TEAEs by intensity Grade ≥ 3** (“3”, “4”, “5” for the “AE most extreme NCI CTCAE grade” field in the “Adverse Event/IRR/MS Relapse” eCRF form)
- **Serious TEAEs** (“Serious” for the “Is this event non-serious or serious?” field in the “Adverse Event/IRR/MS Relapse” eCRF form),
- **Serious TEAE related to study drug**
- **Serious TEAE by intensity Grade ≥ 3**
- **TEAEs that led to study drug discontinuation** (“Drug Withdrawn” for the “Action taken with ocrelizumab due to SAE/AE” field in the “Adverse Event/IRR/MS Relapse” eCRF form)
- **TEAEs that led to modification or interruption of study drug** (“Dose reduced” or “Dose temporarily interrupted” for the “Action taken with ocrelizumab due to SAE/AE” field in the “Adverse Event/IRR/MS Relapse” eCRF form)

- **Non-serious TEAEs reported by 5% or more of patients** (Note: table required for EudraCT and CT.gov disclosure registries)

Adverse events rates per 100 patient-years of exposure are defined as:

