(total number of adverse events/total duration in the study) × 100.

Event rate per 100 PY will be presented on the following events:

- AE with fatal outcome
- infusion related reaction (IRR)
- Serious infusion related reaction (IRR)
- infections (based on SOC)
- serious infection (based on SOC)
- AE leading to study drug discontinuation (“Drug Withdrawn” for the “Action taken with ocrelizumab due to SAE/AE” field in the “Adverse Event/IRR/MS Relapse” eCRF form)
- Serious AE leading to study drug discontinuation (“Drug Withdrawn” for the “Action taken with ocrelizumab due to SAE/AE” field in the “Adverse Event/IRR/MS Relapse” eCRF form)
- AE leading to dose modification/interruption
- Serious AE leading to dose modification/interruption
- AE related to study medication,
- AE of Grade ≥ 3 .

All serious adverse events and deaths will be also listed.

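### The adverse-event epoch tables set two 24-week periods beside one 48-week period with no person-time rate per epoch, so a constant risk could be read as a rising one

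*SAP*

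**What the plan says.** Two epoch displays are planned in SAP 4.6.2, and both use boundaries at Weeks 24, 48 and 96: "An epoch summary (baseline to week 24, week 24 to week 48, and week 48 to week 96) of TEAEs will be repeated".

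- **Overview.** The epoch overview is described as "including the number of events and number and proportion of patients with adverse events emerging and serious AE in each of the period".
- **By SOC and PT.** For all TEAEs, the epoch split gives the number and proportion of patients only.
- **Placement rule.** An AE belongs to a period "if the AE onset date occurred on or after the start date of trial treatment + week X and before start date" plus Y weeks. The clock is nominal weeks from first dose, not actual infusion dates. The SAP adds: "If the emergence of an AE cannot be clearly assigned to a period, the AE will be considered emergent across all appropriate periods".
- **Denominator.** AE summaries use the ITT population. No number at risk per epoch is defined.
- **Exposure-adjusted rate.** It is defined as "total number of adverse events/total duration in the study) × 100", so it runs over the whole study. Eleven event categories receive it, including infections, serious infections and Grade 3 or higher AEs. Overall AEs and overall SAEs are not among them.

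Protocol 6.5.2 says that AE summaries will include rates or incidence rates with 95% CIs.

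On dosing, Protocol Table 1 says "Each dose has a duration of 24 weeks", and SAP 2 has infusions on "i.e., Days 1 and 15) followed by one 600-mg infusion in 500 mL 0.9% sodium chloride every 24 weeks". The first epoch therefore holds Days 1 and 15, the second holds Week 24, and the third holds Weeks 48 and 72. Protocol Appendix 1 allows ±14 days at Weeks 24, 48, 72 and 96.

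**The concern.** A table split by period is read across its columns. Here the last column covers twice the time of each other column, and nothing in the table adjusts for that. Both the expected event count and the chance that a patient has at least one event grow with the length of the window.

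The question of risk over time matters for this drug. Protocol 5.1.1.1 reports that the share of patients with immunoglobulins below the lower limit of normal grew with time and successive dosing, and that a higher risk of serious infection with continued decrease cannot be excluded. A near-doubled SAE or infection proportion in the last epoch is the pattern a reader would take as support for that worry. A real fall in risk could equally go unseen. Apart from the infusion-reaction tables, these are the only planned summary tables of AEs and SAEs over time.

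**Working it through.** The plan gives no figure for these tables, so there is none to reproduce. The check asks what they would show if risk did not change.

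**Inputs.** The epoch lengths are L = 24, 24 and 48 weeks (SAP 4.6.2), and N = 750 (Protocol 3.1.5). The 96-week proportions on ocrelizumab in the pooled Phase III RMS trials (Protocol 1.2) are SAE 6.9%, any AE 83.3%, infection 58.4% and serious infection 1.3%. They serve as planning values only, since they come from another population.

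**Formulas.** The constant weekly hazard is λ = −ln(1 − p96)/96. The proportion with at least one event in an epoch is 1 − exp(−λL), which is 1 − (1 − p96)^(1/4) for 24 weeks and 1 − (1 − p96)^(1/2) for 48 weeks. For SAEs this gives 1 − 0.931^(1/4) = 1.77% and 1 − 0.931^(1/2) = 3.51%.

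| Event | Wk 0-24 | Wk 24-48 | Wk 48-96 | Last/middle | Patients of 750 |
|---|---|---|---|---|---|
| SAE | 1.8% | 1.8% | 3.5% | 1.98 | 13 / 13 / 26 |
| Serious infection | 0.33% | 0.33% | 0.65% | 2.00 | 2 / 2 / 5 |
| Infection | 19.7% | 19.7% | 35.5% | 1.80 | 148 / 148 / 266 |
| Any AE | 36.1% | 36.1% | 59.1% | 1.64 | 271 / 271 / 444 |

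**Event counts.** Expected events are NλL. For SAEs that is 13.4, 13.4 and 26.8, so counts double exactly.

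**A falling hazard.** If the hazard halves after Week 48, (λ/2) × 48 = λ × 24. The last epoch then shows the same proportion as the middle one, and the fall is invisible.

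**Dropout.** With 5% to 20% lost by Week 96 (assumed, constant rate) and a fixed ITT denominator, the last-to-middle ratio is 1.94 to 1.82 for SAEs and 1.61 to 1.52 for any AE.

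**Front-loaded infusion reactions.** Protocol 5.1.1.1 says that these are more frequent at the first infusion. Let q1 be the reaction risk in the first epoch and q the risk at each later infusion (both assumed). Keep the 96-week any-AE total at 83.3%, so that 0.167 = (1 − q1)(1 − q)³ exp(−96λ).
- q1 = 34.3% (the Phase III 96-week reaction figure, all placed in the first epoch) and q = 0 gives 53% / 29% / 50%.
- q1 = 30% and q = 10% gives 47% / 32% / 54%.

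The first-to-last contrast for any AE can thus be flat or reversed. The last epoch still exceeds the middle one.

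**On the person-time scale.** With no dropout, 24 weeks in 750 patients is 750 × 24 × 7/365.25 = 345 patient-years, and 48 weeks is 690. For SAEs, 13.4/345 and 26.8/690 both give 3.9 per 100 patient-years, so the length effect disappears.

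**Nominal cut (secondary).** Take 25 reactions per 100 patients in the first epoch and 10 at each later infusion (assumed). If half of the Week 24 and Week 48 infusions are given early, 25 / 10 / 20 becomes (25 + 5) / (5 + 5) / (5 + 10) = 30 / 10 / 15. Events move to the earlier epoch.

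**The case against.** The best case for leaving the tables alone is that the study is single-arm and mainly descriptive (Protocol 6). The SAP plans no test or comparison between epochs. The column labels show the weeks, listings give study days, and infections and serious infections already have whole-study rates. Event counts can also be added over the first two epochs and set against the third, 48 weeks against 48. That last point stands for AE and SAE event counts, apart from dropout and any event counted in more than one period. It does not help with patient proportions, which cannot be added, or with the SOC and PT table, which has no event counts. Visible labels do not supply the missing rate.

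Three stronger readings are tempting, and the documents do not support them.

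- *The nominal cut contributes to an apparent rise.* It does not. An early Week 24 or Week 48 infusion moves reactions into the preceding epoch, late infusions stay on their own side of the boundary, and Week 72 lies inside the last epoch. The cut misattributes some reactions, and infusion reactions have their own by-infusion tables in SAP 4.6.2.1.
- *The extra dosing visit in the last epoch inflates it against both others.* The first epoch also holds two infusions, and reactions concentrate there.
- *The SAP's rule assigning AEs to doses would solve the problem.* That rule ("only applicable if the AE onset date is on or after the date of the first infusion of that dose") also sends AEs from safety follow-up to the last dose received, and follow-up lasts at least 96 weeks. Delayed doses stretch intervals, and under SAP 4.6.1 a missed dose renumbers later ones. Dose intervals would again differ in length.

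**Conclusion.** The point holds as a defect of display. The epochs differ in length, no per-epoch person-time rate is planned, and no planned rate covers overall AEs or overall SAEs. At a constant hazard the last epoch shows about 1.6 to 2 times the patient proportion of the middle one. The effect is clearest for SAEs and serious infections, where the ratio is close to 2.

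A reader might infer that the tables will show a rise that is not real. The documents cannot support that: there are no epoch results, and the true course could be rising, flat or falling. What can be said is that the tables as specified cannot tell these apart without outside arithmetic.

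The ratios assume the Phase III proportions, a constant hazard equal across patients, and independence between epochs. If events cluster in a few patients, the ratio of proportions is smaller, but event counts still double. No primary or secondary efficacy analysis is affected.

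**What to change.** In both epoch displays of SAP 4.6.2:

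1. Add events per 100 patient-years with 95% CIs for AEs, SAEs, infections and serious infections. Use as denominator the patient-time under observation within that epoch, ending at withdrawal, death or the clinical cut-off date.
2. Base the patient proportions on patients still under observation at the start of the epoch, and print that number in the column header.
3. As an alternative to the rates, split the last epoch into Weeks 48-72 and 72-96 so that all columns span 24 weeks, keeping the at-risk denominator. At constant hazard and without front-loading, the Phase III values would then give about 1.8% for SAEs and 36% for any AE in every column.
4. Add a footnote that epochs follow nominal weeks, so a reaction to an infusion given early in the visit window may fall in the preceding epoch, and refer the reader to the by-infusion tables.

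The rates are the essential part. The change needs SAP wording, some programming on dates already collected, and a few more columns in descriptive tables.

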#### **5.3.5.1 Infusion-Related Reactions**

Adverse events that occur during or within 24 hours after study drug administration and are judged to be related to study drug infusion should be captured as a diagnosis (e.g., "infusion-related reaction" or "anaphylactic reaction") on the Adverse Event eCRF. If possible, avoid ambiguous terms such as "systemic reaction." Associated signs and symptoms should be recorded on the dedicated Infusion-Related Reaction eCRF.

Investigators should consider a local IRR for any symptoms affecting the skin and localized to only one place. Any other IRR should be considered as systemic.

If a patient experiences both a local and systemic reaction to the same dose of study drug, each reaction should be recorded separately on the Adverse Event eCRF, with signs and symptoms also recorded separately on the dedicated Infusion-Related Reaction eCRF.

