2.4 ANALYSIS TIMING

The primary analyses will be performed after the last Confirmed Disease Progression visit occurred. The results of the statistical analyses described in this SAP will be included in a Clinical Study Report (CSR).

The data collected before CCOD (Clinical Cut-off Date) will be included in the primary analysis. The primary efficacy analysis will be performed on the Treatment period, which is defined as being from the first infusion of treatment (day1) until:

The end of the Treatment Period will be the last visit date of any efficacy measurement at week 96 (including EDSS, MRI or PRO) or withdraw date.

The duration of the treatment period is calculated as

$$\text{End of Treatment Period} - \text{first infusion date} + 1.$$

An analysis update of data collected during Safety Follow-up period will be performed once the last patient completed the safety Follow-up period. An addendum to the CSR will include results of selected statistical analyses described in this SAP, if not available at the time of the primary CSR analysis (refer to LoPo for selection of analyses). For each data type collected during the follow-up period (refer to protocol Appendix 2: Follow-up Schedule of Assessments), only listing will be provided if less than 50 patients have data available.

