4.6.1 Exposure of Study Medication

Definitions

Dose: Ocrelizumab dose is given as one infusion or two infusions administered 2 weeks apart. Patients will be considered to have received a Dose of treatment if at least part of one infusion of that Dose (either Day 1 or Day 15 for dual infusions) was given. If a Dose is completely missed instead of delayed, the next dose number will be based on the number of previous doses received.

Treatment duration (in weeks) for a patient will be calculated as follows:

$$[(\text{Date of last contact}^* - \text{Date of first dose}) + 1] / 7$$

Treatment duration (in years) for a patient will be calculated as follows:

$$[(\text{Date of last contact}^* - \text{Date of first dose}) + 1] / 365.25$$

*Earliest 1) date of last contact from the study completion page or study early termination page

2) date of death

3) CCOD

Exposure Analysis

Exposure of ocrelizumab will be summarized using descriptive statistics with the following data:

- treatment duration (weeks),
- number of doses received (day 1 and day 15 infusions are considered as one dose)
- total cumulative dose (mg).

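### Six adverse-event rates per 100 patient-years are understated because their denominator includes off-drug follow-up, in which the events cannot arise

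*SAP*

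**What the plan says.** SAP 4.6.2 introduces the rates with "Adverse events rates per 100 patient-years of exposure are defined as" and then gives the formula "total number of adverse events/total duration in the study) × 100". It applies this one formula to eleven event types. Six depend on dosing: IRR, serious IRR, AE and serious AE leading to study drug discontinuation, and AE and serious AE under "AE leading to dose modification/interruption". The other five are fatal AEs, infections, serious infections, drug-related AEs and Grade 3 or higher AEs.

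The SAP does not define total duration in the study. The nearest definition, treatment duration in SAP 4.6.1, ends at the earliest of "date of last contact from the study completion page or study early termination page", death or the clinical cut-off, so it does not stop when dosing stops.

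SAP section 2 sets the dosing course: "Treatment period: Open-label treatment period of 96 weeks (last dose administered at Week 72". It also says "Patients who discontinue treatment early will be followed up for at least 96 weeks after the Early Treatment Discontinuation Visit", and gives the same minimum to completers who do not join the extension study. Protocol 5.3.5.1 describes IRRs as "Adverse events that occur during or within 24 hours after study drug administration and are judged to be related to study drug infusion". SAP 4.6.2 identifies the discontinuation and dose-change AEs from the recorded action taken with ocrelizumab (drug withdrawn, dose reduced, or temporarily interrupted).

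**The concern.** A person-time rate is interpretable when the time counted is time at risk. A patient in safety follow-up receives no ocrelizumab (Protocol Appendix 2 schedules none), so that patient cannot have an infusion reaction and has no study dose left to withdraw, reduce or interrupt. Each week of follow-up lowers the six rates without any change in risk.

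The error runs one way: it makes tolerability look better. It also makes the rates depend on what patients choose after treatment, because those who join the extension study or move to commercial drug add no follow-up time. The exposure label gives the reader no warning. SAP 4.4.2.5 uses a different time for the relapse rate, where drug exposure means the length of the treatment period.

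**Working it through.** The documents state no expected AE rate, so there is no planned figure to reproduce. The check is how far the stated denominator departs from on-treatment time.

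**Inputs from the documents**
- Treatment period 96 weeks, last dose Week 72, follow-up at least 96 weeks (SAP section 2).
- Enrolment about 12 months (Protocol 3.2).
- A Week 96 EDSS change is confirmed after a further 24 weeks (Protocol 3.1.3), and the primary analysis waits for the last confirmation visit (SAP 2.4).

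**Assumptions (not in the documents)**
- A share pe = 5-12% stops treatment at about Week 40, and 80% of these are followed.
- A share pf = 5-30% of completers enters follow-up.
- Follow-up accrued by the primary cut-off is about 50 weeks for completers (mean 26 weeks from staggered enrolment plus 24 weeks to the last confirmation) and about 90 weeks for early stoppers.

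**Formula, in mean weeks per patient**
- On-treatment = (1 − pe)·96 + pe·40
- Follow-up = (1 − pe)·pf·50 + pe·0.8·90
- Shortfall = 1 − on-treatment/(on-treatment + follow-up)

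| pe | pf | On-treatment | Follow-up | Shortfall at primary cut-off |
|---|---|---|---|---|
| 5% | 5% | 93.20 | 2.375 + 3.60 = 5.975 | 1 − 93.20/99.175 = 6.0% |
| 5% | 30% | 93.20 | 14.25 + 3.60 = 17.85 | 1 − 93.20/111.05 = 16.1% |
| 12% | 5% | 89.28 | 2.20 + 8.64 = 10.84 | 1 − 89.28/100.12 = 10.8% |
| 12% | 30% | 89.28 | 13.20 + 8.64 = 21.84 | 1 − 89.28/111.12 = 19.7% |

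If nobody enters follow-up, the shortfall is zero.

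**With full follow-up.** If the same rates were recomputed after all follow-up (96 weeks in place of 50 and 90), the two extreme rows become 1 − 93.20/101.60 = 8.3% and 1 − 89.28/123.84 = 27.9%.

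**Single patient.** Someone who stops at Week 24 and completes 96 weeks of follow-up contributes 120 weeks against 24 on treatment, five times the time at risk. Stopping at Week 48 gives 144 against 48, three times.

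**Scale of the rates (illustration).** Take 750 patients who all complete 96 weeks, with one event per affected patient at the Phase III RMS percentages in Protocol 1.2 (IRR 34.3%, discontinuation for AEs 3.5%).
- On-treatment person-years = 750 × 96 × 7/365.25 = 1379.9.
- IRR: 257.25/1379.9 = 18.6 per 100 patient-years.
- Discontinuation: 26.25/1379.9 = 1.90 per 100 patient-years.
- If 10% add a full 96 weeks of follow-up, person-years are 1379.9 × 1.10 = 1517.9, and the same events give 16.9 and 1.73, a fall of 9%.
- Per infusion, at five infusions each, IRR is 257.25/3750 = 6.9 per 100 infusions, whatever the follow-up.

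**The case against.** The strongest counter-argument is that little depends on these rates. The study is single-arm and descriptive, and the formula is stated openly. SAP 4.6.1 itself counts time to last contact under an exposure heading. SAP 4.6.2.1 already shows IRRs by infusion, by intensity and by previous DMT, and SAP 4.6.2 gives event and patient counts for all six categories. None of those displays uses person-time. This stands as a limit on the consequence. It does not correct the rates the SAP says it will present, and the discontinuation and dose-change events have no other time-based rate.

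A reader might infer that the rates will fall between the primary report and the follow-up addendum. SAP 2.4 does plan one: "An analysis update of data collected during Safety Follow-up period will be performed once the last patient completed the safety Follow-up period". But it restricts the addendum to selected analyses not already available for the primary report, and these rates will be available by then. The 8% to 28% range applies only if they are repeated.

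A reader might also infer that comparisons across prior-DMT subgroups are distorted. The SAP repeats the TEAE summary by last DMT but does not say that the rates per 100 patient-years are repeated.

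Nor are all six events confined to infusion days. That holds for IRRs. An AE leading to withdrawal or interruption may begin between infusions, so its risk period is the dosing course.

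Finally, a completer has no further study dose after Week 72, so counting Weeks 72 to 96 as on-treatment is partly convention. It follows the statement under Protocol Table 1 that each dose lasts 24 weeks.

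**Conclusion.** The point holds for six of the eleven rates. Their label promises exposure time, their denominator includes time off drug, and no other SAP text stops the clock at the end of dosing. The direction is certain once any patient enters follow-up: the rates are too low.

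The size is not known. The 6% to 20% rests entirely on the assumed shares, and a high uptake of the extension study or of commercial drug would bring it towards zero. The percentage is measured against on-treatment patient-years; for the two IRR rates the better reference is the number of infusions, so it describes them only loosely.

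Total study time is defensible for fatal AEs, infections, related AEs and Grade 3 or higher AEs, which can occur off drug and are collected through follow-up (Protocol 5.3.1).

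**What to change.** In SAP 4.6.2:
- Divide the four discontinuation and dose-modification rates by treatment-period person-time, the length defined in SAP 2.4 and already used as drug exposure in SAP 4.4.2.5. State that the clock ends at treatment discontinuation for early stoppers. SAP 2.4 ends it at Week 96 or a withdrawal date, without saying whether that means withdrawal from treatment or from the study.
- Report IRR and serious IRR per 100 infusions given.
- Keep total study time for the other five rates, define it, and label it as time in study.

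The cost is a wording change and two extra denominators from dates already collected. The stated rates for the four discontinuation and dose-modification categories become slightly higher. No visit, assessment or clinical rule changes.
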